# Design of the pilot, proof of concept REMOTE-COVID trial: REmote MOniToring usE in suspected cases of COVID-19 (SARS-CoV 2)

## A trial protocol

[name]1\*, [name], [name], [name], [name], [name]

- 1) Division of Surgery & Cancer, [name]
- 2) West Middlesex University Hospital, [name]

Clinical trials registration information: ClinicalTrials.gov Identifier: NCT04337489

16 March 2020

16 Abstract:

17 Background: The outbreak of SARS-CoV-2 (coronavirus, COVID-19), declared a pandemic by the  
18 World Health Organisation (WHO) is global health problem with ever-increasing attributed deaths.  
19 Vital sign trends are routinely used to monitor patients with changes in these parameters often  
20 preceding an adverse event. Wearable sensors can measure vital signs continuously (e.g. heart rate,  
21 respiratory rate, temperature) remotely and can be utilised to recognise early clinical deterioration.

22 Methods: We describe the protocol for a pilot, proof-of-concept, observational study to be  
23 conducted in an engineered hotel near London airports, United Kingdom. The study is set to  
24 continue for the duration of the pandemic. Individuals arriving to London with mild symptoms  
25 suggestive of COVID-19 or returning from high risk areas requiring quarantine, as recommended by  
26 Public Health England, or healthcare professionals with symptoms suggestive of COVID-19 unable to  
27 isolate at home will be eligible for a wearable patch to be applied for the duration of their stay.  
28 Notifications will be generated should deterioration be detected through the sensor and displayed  
29 on a central monitoring hub viewed by nursing staff, allowing for trend deterioration to be noted.  
30 The primary objective is to determine the feasibility of remote monitoring systems in detecting  
31 clinical deterioration for quarantined individuals in a hotel.

32 Discussion: This trial should prove the feasibility of a rapidly implemented model of healthcare  
33 delivery through remote monitoring during a global pandemic at a hotel, acting as an extension to a  
34 healthcare trust. Potential benefits would include reducing infection risk of COVID-19 to healthcare  
35 staff, with earlier recognition of clinical deterioration through ambulatory, continuous, remote  
36 monitoring using a discrete wearable sensor. We hope our results can power future, robust future  
37 randomised trials.

38 Trial registration: ClinicalTrials.gov Identifier: NCT04337489

39 Keywords: remote sensing technology; protocol; clinical trial; patient deterioration; monitoring,  
40 ambulatory.

41 Background:  
42 The recent outbreak of SARS-CoV-2 (COVID-19), declared a pandemic by the World Health  
43 Organisation (WHO) and a growing global health problem, has stretched resources, creating  
44 pressures within the National Health Service (NHS) with implications for patient safety. UK Chief  
45 Medical Officers have raised the risk to the UK to high, with ever increasing confirmed cases and  
46 attributed deaths.

47 High risk travellers with suspected or confirmed cases of COVID-19 are likely to transferred  
48 immediately to hospital. However, travellers with milder symptoms or returning from high risk  
49 areas, a two-week period of observation/quarantine may be required, in accordance with Public  
50 Health England recommendations. The rate of clinical deterioration for individuals suffering with  
51 COVID-19 remains unknown; given that widespread vaccine deployment remains imminently  
52 unforeseeable, novel strategies are required in approaching this pandemic.

53 Vital signs trends (heart rate, respiratory rate, blood pressure, temperature, oxygen saturations) are  
54 routinely used for monitoring hospital patients. Clinical deterioration may be recognised through  
55 changes in these parameters, and often precedes an adverse event. As such, The National  
56 Institute for Health and Care Excellence (NICE) and the Royal College of Physicians (RCP) recommend  
57 that all patients have their vital signs recorded every 12h as a minimum.

58 Across the National Health Service (NHS), the use of the National Early Warning Score 2 (NEWS), a  
59 'track and trigger' warning score, has been implemented in accordance with the RCP to guide on  
60 escalation protocols and monitoring frequency of vital signs. Accordingly, heart rate (HR),  
61 respiratory rate (RR), temperature, blood pressure, oxygen saturations, and level of consciousness  
62 are assessed every 4-6 hours with more frequent monitoring for acutely unwell patients.

63 Progression in non-invasive digital technologies have renewed potential for remote monitoring  
64 solutions. Wearable sensors offer an opportunity for sensor alerting systems to continuously  
65 monitor vital parameters remotely, recognise early deterioration and support clinical decision

66 making, allowing people to receive monitoring outside of expensive hospital facilities; in resource  
67 limited hospitals; and utilising alternate sites in crisis scenarios.

68 Previous studies have demonstrated acceptability and practicability of continuous monitoring using  
69 wearable sensors on general surgical and medical wards in the UK and The Netherlands. Initial  
70 work by Downey et al. were limited by imbalanced randomisation leading to significant baseline  
71 differences across the two trial arms and failure to adjust for these in their analyses. Nevertheless,  
72 the wearable sensor seemed to demonstrate feasibility in hospital settings. Qualitative analyses,  
73 through semi-structured interviews for patients and healthcare staff, similarly favoured continuous  
74 the notion of continuous vital sign monitoring in general wards. It should be noted that many of  
75 the patients interviewed were admitted for malignant disease which is likely to influence qualitative  
76 outcomes. Delivery of healthcare outside of hospital facilities (e.g. in hotels) is theoretically possible  
77 through continuous remote monitoring of vital signs but has yet to be studied; given the global  
78 pandemic and fear of future waves, evaluation of its viability is justified.

79 Here, we describe the design of our pragmatic trial, exploring the feasibility of remote monitoring  
80 systems in suspected cases of COVID-19 at a hotel, primarily as earlier recognition of clinical  
81 deterioration.

82 Methods:

83 *Overall design:*

84 This pragmatically designed, pilot, proof-of-concept, observational study was reviewed and  
85 approved by London – Queen Square Research Ethics Committee (IRAS: 281757) and this protocol  
86 was developed in accordance with recommendations from the Standard Protocol Items:  
87 Recommendations for Interventional Trials (SPIRIT) guidelines. The objective is to determine the  
88 feasibility of remote healthcare delivery in a hotel with rapid implementation in the COVID-19 era.  
89 Feasibility will be tested through rate of participation and number of vital alerts generated.

90 The SensiumVitals™ (Sensium Healthcare Ltd., United Kingdom) system can be engineered in the  
91 building (hotel) for use with the wearable sensor. All participants would be fitted with the sensor on  
92 arrival and would always be worn. A designated area within the facility would act as a central hub  
93 allowing for remote monitoring to occur by healthcare staff. Alerts would be generated, in  
94 accordance with NEWS parameters (Table 1) but can be individually tailored, to identify  
95 deteriorating participants. Participants can be escalated to hospitals should rapid deteriorating in  
96 vital signs be noted; ambulance services and paramedics will be present on site to facilitate this. The  
97 decision to escalate will come from a senior nurse, present on site, or a general practitioner  
98 contactable at all times.. The temperature alert threshold was lowered to the lowest score in the  
99 NEWS chart, allowing for earlier detection and improved sensitivity; this decision was made from  
100 previous work which demonstrated varying limits of agreement for temperature when compared to  
101 nursing observations. Escalation protocols will be developed and trialled, allowing staff to address  
102 issues as they arise (Figure 1).

103 *Wearable sensor system*  
104 SensiumVitals™ by the Surgical Company, have produced a lightweight, waterproof, single-use,  
105 wearable wireless ‘patch’ with a battery life of 5 days measuring vital signs every two minutes. The  
106 sensor attaches to an individual’s chest with two ECG electrodes, recording HR, RR, and a wire  
107 attaches around the individual’s back, measuring axillary temperature. The sensor is FDA approved  
108 and CE marked. Data are transmitted through radiofrequency and dedicated intranet hotspots.  
109 Physiological parameters can be viewed by clinical staff on a mobile device/desktop computer,  
110 allowing trends towards deterioration to be noted, with tailored alerts generated for deteriorating  
111 individuals in accordance with NEWS (Figure 2).

112 All sensor data collected by the SensiumVitals® system will be stored on a created secured hotel  
113 network; access to which is restricted to research personnel. Given that the hotel acts as an

114 extension to a healthcare trust, the SensiumVitals® system inherits all the hospital procedures and  
115 data backup policies, ensuring data access and servers are secured.

116 In line with the principles of Good Clinical Practice guidelines, data will be securely archived for a  
117 minimum of 5 years.

118 Following the completion of quarantine, participants will be invited to share their experiences  
119 through using semi-structured interviews and questionnaires. Individual interviews allow for  
120 anonymity and truthful perceptions/attitudes. This method enables narratives to be elicited through  
121 guided but open questioning.

122 *Hypotheses:*

123 1) Continuous remote monitoring with wearable sensors of vital signs will identify  
124 deteriorating patients.  
125 2) Healthcare provision in a hotel will be feasible and acceptable amongst healthcare staff  
126 and participants.

127 *Sequence of events:*

128 Patching patients and using data for academic research

129 1. Eligible participants from the airport will be transferred to the hotel by paramedics.  
130 2. Upon arrival to the engineered hotel, an initial assessment of all participants will be  
131 undertaken. A study information sheet will be provided, and informed consent taken for  
132 wearable sensors to be applied, allowing remote monitoring of vital signs. To ensure  
133 appropriate quarantine.  
134 3. In a designated area within the building, a central monitoring hub will be set up to monitor  
135 the recorded parameters by National Health Service (NHS) healthcare staff from a local  
136 Trust. The hub contains a site manager, porters, security staff, nurses, ambulance services,  
137 professional cleaners, and hotel staff.

138 4. If a participant deteriorates, an alert should be generated on a smartphone device/desktop  
139 computer; following this, an escalation protocol will be trialled to action the alert in an  
140 appropriate manner; hospitalisation may be necessary. Initially, nursing staff will gather  
141 more information through telephone review. Following this, a virtual GP can be contacted  
142 for further advice. Ambulance services and paramedics will be on-site to facilitate  
143 hospitalisation should rapid deterioration occur. These healthcare professionals are  
144 independent and can provide oversight.

145 5. Participants will be invited for an interview and be asked to complete a survey on their  
146 experiences following quarantine completion.

147 6. Participant care records will be stored on an online Care Information Exchange system  
148 (compliant with General Data Protection Regulation) that is currently in place across the  
149 trust. Electronic health records and patient notes will be reviewed to determine clinically  
150 relevant events if transfer to hospital occurs (e.g. hospital length of stay, mortality,  
151 escalation to ITU).

152 7. Sensor data will be extracted from the central servers containing sensor data for appropriate  
153 statistical analyses for associated clinical efficacy of health outcomes in COVID-19.

154

155 Semi-structured interviews/Questionnaires (mixed methods)

156 1. All participants alongside healthcare staff will be invited to take part in semi-structured  
157 interviews and be given questionnaires. These will take place by the primary lead researcher  
158 using prepared topic guides.

159 2. Written consent will be obtained from those who agree to participate.

160 3. An audio recording will be made of the interviews. Notes reflecting verbal responses may be  
161 taken. The interviews will be conducted at the engineered hotel.

162 4. The recordings will be transcribed, and the data will undergo thematic analyses.

5. Validated and unvalidated questionnaires will also be given enquiring about experiences (e.g. PHQ-9, GAD-7, satisfaction, anxiety related to the devices).

165

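### Do the hotel-based, end-of-quarantine interviews and the lack of a planned split by participant type undermine the acceptability findings?

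*Combined protocol and SAP*

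**What the plan says.** All references are to the combined protocol and SAP.

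- **Timing.** Under Wearable sensor system: "Following the completion of quarantine, participants will be invited to share their experiences". Item 5 of Sequence of events repeats it, asking about "experiences following quarantine completion".
- **Place.** Semi-structured interviews/Questionnaires, item 3: "The interviews will be conducted at the engineered hotel".
- **Who is invited.** Item 1 of the same list: "All participants alongside healthcare staff will be invited to take part in semi-structured" interviews, with questionnaires given as well. Item 2: "Written consent will be obtained from those who agree to participate".
- **Questionnaires.** Item 5: "Validated and unvalidated questionnaires will also be given enquiring about experiences". No place or mode is attached to them.
- **Transfer to hospital.** It is foreseen under Overall design ("Participants can be escalated to hospitals should rapid deteriorating in" vital signs be seen) and in Sequence of events, item 4 ("hospitalisation may be necessary"). Item 6 adds a review of the clinical records of anyone transferred.
- **Analysis.** Questionnaire answers are to be shown as frequency distributions and interviews analysed thematically. The text mentions neither pooling nor splitting by participant type.
- **Status.** Acceptability and usability form the second exploratory outcome under Outcomes and progression criteria. Overall design tests feasibility through participation and alerts.
- **Stated limitation.** The Discussion says that healthcare professionals enrolled as participants may report more favourably because they are used to monitoring.

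**The concern.** Read literally, the timing and place suit a person who stays in the hotel until quarantine ends. A person moved to hospital does not fit that description, and the only procedure written specifically for such people is the record review, which captures no experience. They are also the participants on whom the escalation pathway acted most fully, so losing their views could leave the acceptability account resting on those for whom little happened.

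The second strand is similar. The authors name a source of bias and record participant type at entry through the inclusion criteria, but promise no display by type. A single distribution could then reflect the mix of healthcare professionals and travellers more than what either group thought.

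At stake is the participant half of the acceptability claim in hypothesis 2, and the Discussion's expectation that these data will inform wider use of the technology.

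**Working it through.** There is no planned figure to reproduce, since no acceptability threshold, transfer rate or participant mix is given, and the Background says the rate of deterioration is unknown. The check is therefore a reading of the text, followed by illustrations on stated assumptions.

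**1. Does the text exclude transferred participants?** The invitation covers all participants. The timing follows quarantine and the interview place is the hotel. The questionnaire has no fixed place. The documents do not say whether a transferred person returns to the hotel, or that transfer ends eligibility for interview. The statements are compatible. What is missing is operational detail for the interview only.

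**2. How often could the gap arise?** Take n = 10, the minimum in the participation-rate calculation, and an assumed, independent transfer probability p. The chance of at least one transfer is 1 − (1 − p)^n and the expected number is np. The 10 may mean people approached. At the 90% participation the protocol expects, that gives 10 × 0.9 = 9 fitted with a sensor, so both are shown.

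| p (assumed) | Expected transfers, n = 10 | P(at least one), n = 10 | P(at least one), n = 9 |
|---|---|---|---|
| 2% | 0.2 | 18% | 17% |
| 5% | 0.5 | 40% | 37% |
| 10% | 1 | 65% | 61% |
| 20% | 2 | 89% | 87% |

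Nothing in the documents anchors p. Entrants have mild symptoms or are quarantined returnees, and high-risk travellers who need hospital go there directly and are ineligible.

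**3. What could a missing interview do?** If k of 10 are not interviewed and all the others are favourable, the observed 100% is compatible with a true proportion from (10 − k)/10 to 1: 90% to 100% for k = 1 and 80% to 100% for k = 2. This assumes everyone else agrees to a voluntary interview. By comparison, the exact (Clopper-Pearson) 95% interval for 4 of 8 is 16% to 84%. Sampling uncertainty is much the larger of the two.

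**4. What would a split by type show?** Assume, purely for illustration, 95% favourable among healthcare professionals and 70% among travellers. With healthcare professionals a share w of the sample, the overall rate is 0.95w + 0.70(1 − w):

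- w = 0.2: 0.19 + 0.56 = 75%
- w = 0.5: 0.475 + 0.35 = 82.5%
- w = 0.8: 0.76 + 0.14 = 90%

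So the mix can matter in principle. But with 10 people the smaller group has at most 5. The exact 95% interval for 5 of 5 is 48% to 100%, since the lower limit is 0.025^(1/5) = 0.478, and for 0 of 5 it is 0% to 52%. A split at that size cannot separate the groups or remove the bias, and the cells could identify people. Suppressing them could empty much of the table.

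**The case for a change.** The best case for a change is that inviting all participants is only as good as the means of reaching them. Existing contacts do not obviously serve: the telephone review in Sequence of events is a clinical response to an alert, and the email addresses under Patient and public involvement are optional and meant for sharing results. Written consent is needed, and is easier to arrange before a transfer than after it. The protocol also holds others to this standard: its Background notes that earlier qualitative findings were probably coloured by who was interviewed. Staff interviews do not fill the gap, because they concern those delivering care and not healthcare professionals enrolled as participants.

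Much of this stands. No remote interview option is written, and readers will want to know who answered. It does not show that the plan yields a wrong or misleading result. The questionnaire route remains open, and nothing bars a remote interview with a willing participant or a display by type where numbers allow. The healthcare-professional bias, with its likely favourable direction, is already disclosed. For transferred participants, the direction of any effect is unknown.

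**Conclusion.** No change to the plan follows. The protocol leaves unsaid how an interview would reach someone who has left the hotel, and it does not promise results by participant type. The first is a practical detail that the study team can settle when a transfer occurs, and if no one is transferred it never arises. The second is a defensible choice in a descriptive pilot with a stated minimum of 10 people, where a split would be too thin to support any conclusion. Ordinary good reporting covers both: responders out of all those fitted with a sensor, the reason for leaving, and counts by type where disclosure allows.

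No feasibility outcome, progression criterion or stated figure is affected. The effect on the acceptability findings cannot be sized from the documents. The 18% to 89% range for at least one transfer among 10 rests wholly on assumed probabilities of 2% to 20% and on independence between participants.

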## 191 Inclusion Criteria

192 • Aged 18 years or over.

- Able to provide written consent.
- Travellers returning with milder symptoms suggestive of COVID-19 or returning from high risk areas requiring quarantine, as recommended by Public Health England.
- Healthcare professionals with milder symptoms suggestive of COVID-19 unable to isolate at home.

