## 346 Figure legends:

347 Figure 1: Potential escalation pathway; NEWS: National Early Warning Score; GP: general

348 practitioner.

349 Figure 2: Monitoring system for SensiumVitals™ Wearable Sensor

350 Table:

351 *Table 1: Criteria for generating vitals alert*

Parameter	Alert threshold
Respiratory rate (breaths per minute)	$\geq 25$
Temperature (Celsius)	$\geq 38.1$
Heart rate (beats per minute)	$\geq 131$

352

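### Alerts fire on absolute limits and are not split by arrival status, so an abnormality present at entry can count towards the 5-alert target and be read as support for Hypothesis 1

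*Combined protocol and SAP*

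**What the plan says.** **Objective and test.** The Abstract makes the feasibility of detecting clinical deterioration the primary objective. Overall design tests feasibility through the participation rate and the number of alerts. Feasibility outcome 2 counts alerts that follow an abnormal vital sign, gives raised temperature as its example, and sets a minimum of 5. Hypothesis 1 is that "Continuous remote monitoring with wearable sensors of vital signs will identify" patients who are deteriorating.

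**How alerts are described.** The Abstract says "Notifications will be generated should deterioration be detected through the sensor and displayed" on the central hub. Overall design says alerts follow "accordance with NEWS parameters (Table 1) but can be individually tailored, to identify" participants who are deteriorating. Step 4 of the sequence of events says "If a participant deteriorates, an alert should be generated on a smartphone device/desktop" computer.

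**What triggers an alert.** Table 1, "Criteria for generating vitals alert", lists three limits: respiratory rate 25 or more, temperature 38.1 or more, heart rate 131 or more. On temperature, Overall design adds: "The temperature alert threshold was lowered to the lowest score in the" NEWS chart.

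**Who enters, and when monitoring starts.** One inclusion route is "Healthcare professionals with milder symptoms suggestive of COVID-19 unable to isolate at home". The traveller route accepts either milder symptoms or return from a high risk area. The sensor is fitted on arrival. Step 2 says "Upon arrival to the engineered hotel, an initial assessment of all participants will be" carried out, without saying whether it records vital signs.

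**Analysis.** The statistical paragraph after the exclusion criteria describes total alerts, the proportion actioned and the resulting actions.

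**The concern.** Deterioration is a change from an earlier state. The default alert rule records a level. The two differ most in people who are already unwell when the sensor goes on, and the entry criteria admit such people. Under the default limits, a participant at or above 38.1 on arrival can generate an alert while stable or improving.

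The plan does not define deterioration relative to arrival, sets no baseline window, and does not divide alerts into those present at entry and those that are new. A report that met the target of 5 could therefore rest partly or wholly on abnormalities that participants brought with them. The authors also hope that the results will inform the power of later randomised trials. An alert rate that mixes entry illness with new worsening is a poor input for that.

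**Working it through.** **1. The plan's own figures.** The only calculated figure is the participation precision: 1.96 × √(0.9 × 0.1 / 10) = 0.186, against the stated 18%. It does not bear on this point. The target of 5 alerts has no derivation to reproduce.

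**2. The text side by side.**

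| Element | What the plan gives | Link to arrival state |
|---|---|---|
| Objective, Hypothesis 1 | Detecting or identifying deterioration | Implied, not defined |
| Alert rule (Table 1) | Fixed limits on three parameters | None |
| Tailoring (Overall design) | Permitted | No rule, trigger or record stated |
| Start of monitoring | On arrival | No baseline window |
| Arrival assessment (step 2) | Done for all | Not used to classify alerts |
| Feasibility outcome 2 | At least 5 alerts | None |
| Analysis | Totals, proportion actioned, actions | No split |

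No step in this chain takes an arrival abnormality out of the count.

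**3. How far this could matter (illustration only).** Two inputs are missing: q, the share of participants beyond a limit at fitting, and the rule for repeat alerts. I assume 10 monitored participants (the stated minimum sample), independence between them, and default limits throughout.

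*(a) One alert per participant abnormal on arrival.* The number of arrival alerts is binomial (10, q). The chance that these alone reach 5 is P(X ≥ 5):

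| q | 10% | 20% | 30% | 50% | 70% |
|---|---|---|---|---|---|
| P(X ≥ 5) | 0.002 | 0.033 | 0.15 | 0.62 | 0.95 |

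*(b) Every above-limit reading makes an alert.* Readings come every 2 minutes, so five consecutive readings span 4 × 2 = 8 minutes. One participant with a steady fever on arrival would then meet the target alone. The chance of at least one such participant is 1 − (1 − q)^10:

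| q | 10% | 20% | 30% | 50% |
|---|---|---|---|---|
| P(X ≥ 1) | 0.65 | 0.89 | 0.97 | >0.99 |

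The answer runs from negligible to near certain, depending on two inputs that the documents do not give. The tables show that the target cannot be interpreted without the split. They do not estimate the effect in this trial.

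**The case against.** The strongest reply is that outcome 2 does not claim to count deterioration. It counts alerts that follow abnormal vital signs. As a check that sensor, network and hub work, a fever on arrival that triggers an alert is a proper success. This stands, and it is why outcome 2 need not change. It does not settle Hypothesis 1, because no other outcome bears on that hypothesis quantitatively.

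A reader might infer more than the documents support:

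- *That everyone is enrolled because of symptoms.* Travellers can qualify solely by coming from a high risk area.
- *That the plan formally classes an arrival fever as deterioration.* No outcome counts deterioration events. The step 4 sentence runs from deterioration to alert, not the reverse. The Abstract and Overall design come closer, but the equation remains an inference from how alerts are described.
- *That a fever at fitting is certain to alert.* Limits may be tailored, and no persistence, averaging or repeat rule is given.
- *That only new crossings can count.* Someone above a limit at fitting who then gets worse has deteriorated, and must not be discarded.

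Staff can also view trends, telephone review follows an alert, and records are examined after a hospital transfer. These give clinical context, but none is used to classify an alert against baseline. Because the sensor data are stored, the split could be made later. That keeps the cost of the fix low, but it does not replace defining the split in advance.

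**Conclusion.** The point holds in a limited form. The alert count is a main test of an objective about detecting deterioration, yet under the default limits it can include abnormalities present at entry, and the planned analysis does not tell the two apart. This rests on the limits not being tailored in a way that removes such alerts; the documents neither rule that out nor say how it would be done or recorded. The size is unknown, since the share abnormal on arrival and the repeat-alert rule are not given. This does not invalidate a descriptive pilot. It is an inexpensive improvement that should be made so that the alert result bears on Hypothesis 1.

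**What to change.** Keep outcome 2 as a count of all alerts, labelled as a check that the system works. Add to the statistical analysis section:

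1. **Baseline.** For each participant and parameter, define baseline from a stated initial window of sensor readings, plus the arrival assessment if it records vital signs.
2. **Classification.** Report alerts by parameter and as (a) already beyond the limit at baseline or (b) a new crossing after being within the limit.
3. **Worsening within (a).** Report separately any further worsening from baseline in these participants, using a criterion fixed before the data are examined. The protocol itself notes variable agreement between sensor temperature and nursing observations, so the criterion should allow for measurement error.
4. **Units.** Report both the number of alerts and the number of participants alerting, and state how repeat alerts are counted.
5. **Tailoring.** Record every change to a participant's limits, with its time, and classify alerts against the limits then in force.
6. **Inference.** Treat (b) and the worsening within (a), not the total alert count, as the evidence for Hypothesis 1.

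Live alerting, the limits and the staff response stay as they are. The two-minute readings are already stored and extracted, so the cost is a short addition to the analysis text, a log of tailored limits and some extra tabulation. The downside is a smaller count in support of Hypothesis 1.
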